5.7 New Information

Study subjects will be informed of new information that becomes available during the course of this study by their treating physician. Subjects will be notified, at a minimum, in accordance with the IRB/EC's procedure for providing updated information to clinical study subjects, if applicable.

5.8 Study Exit

The subject will be seen by the treating physician according to standard care following intracranial aneurysm treatment. One year post-procedure, the subject will exit the study and be exempt from further data collection.

5.9 Termination of Subject Participation

Subjects may withdraw from the study at any time without penalty or loss of medical care, or they may be withdrawn at any time at the discretion of the principal investigator (PI) or Sponsor for safety or administrative reasons.

5.9.1 Subject Withdrawal

All enrolled subjects have the right to withdraw their consent at any time during this study. All data collected until the time of subject withdrawal will remain in the study database and will be used for analysis. Whenever possible, the site staff should obtain written documentation from the subject who wishes to withdraw his/her consent for future follow-up visits. If the site staff is unable to obtain written documentation, all information regarding the subject's withdrawal must be recorded in the subject's medical record. In addition, the appropriate eCRFs must be completed for the subject to ensure clear documentation of the subject's withdrawal.

5.9.2 Subject Discontinuation by Investigator

An investigator may discontinue a subject from the study, with or without the subject's consent, for any reason that may, in the investigator's opinion, negatively affect the well-being of the subject should they continue in the study. If a subject is withdrawn from the study, the investigator will promptly inform the subject and Sponsor.

5.9.3 Lost to Follow-up

A subject will be considered lost to follow-up if the subject cannot be reached after three (3) attempts to contact the subject for a follow-up visit. The site must document a minimum of three (3) attempts, and the final documented attempt should be made via registered letter.

5.10 Deviations to the Investigation

A protocol deviation is defined as an event where the investigator or study personnel did not conduct the study according to the clinical protocol. Deviations shall be reported to the Sponsor regardless of whether medically justifiable actions are taken to protect the subject in an emergency.

Except for a change that is intended to eliminate an immediate hazard to a subject, the protocol will be followed as described. Subject specific deviations and non-subject specific deviations will be reported. Investigators will also adhere to procedures for reporting study deviations to their IRB/EC in accordance with their specific IRB/EC's reporting policies and procedures, if applicable.

Sites with a high rate of protocol deviations will be closely evaluated and are expected to implement corrective actions to prevent further deviations. If a site demonstrates persistent deviations, as described above, the site may be terminated.

5.11 Discontinuation by IRB/EC

Where applicable, the IRB/EC may choose to discontinue the study at any center(s) for which they granted approval if:

- The research study is not conducted in accordance with the IRB/EC's requirements.
- The research study indicates unexpected serious harm to subjects.

5.12 Study Discontinuation by Sponsor

The Sponsor may choose to discontinue the study if the Sponsor discovers additional information during the study that may cause harm to subject or negatively affect subject safety.

If the study is terminated prematurely or suspended, the Sponsor will promptly inform all clinical investigators of the termination or suspension and the reason(s) for this. Where applicable, the IRB/EC will also be informed, either by the Sponsor or investigator if a local IRB/EC is utilized, promptly and provided with the reasons(s) for the termination. If applicable, regulatory authorities will be informed. Enrolled subjects will be asked to complete all remaining study visits and the subject will then be seen by the treating physician according to standard care following intracranial aneurysm treatment.

6 ADVERSE EVENTS

The following Adverse events will be collected during the course of the study on the eCRFs.

- All Adverse Events (AE) with an underlying neurological cause (Neurological Adverse Events)
- All Device Related Adverse Effects
- All Procedure Related Adverse Events
- All Bleeding Events
- All Serious Adverse Events (SAEs)

Adverse event status will be evaluated throughout the study. These will include events occurring from the point of enrollment until a subject exits the study. If the subject is enrolled and the study procedure is attempted, but the Pipeline™ Flex Embolization Device with Shield Technology™ is not implanted for any reason, subjects will be followed to discharge and relevant safety events will be collected. Investigators must obtain all information available to determine the causality and outcome of the AE and to assess whether it meets the criteria for classification as a serious and/or

unexpected event requiring notification to the Sponsor, and, where applicable, regulatory agency and IRB/EC, within the specified reporting timeframe. AEs will be categorized using the definitions in **Section 6.1**.

All study AEs, as well as the treatment and follow-up required, should be documented in the subject's medical records and in the eCRF. All study SAEs that occur during the 1 year follow-up period will be followed by the investigator until resolution or until 30 days after the occurrence of that event. A list of potential anticipated adverse events is provided in **Section 10.2**.

Bleeding events will be captured as Adverse Events by the sites and will be graded according to the GUSTO⁴⁴ bleeding criteria as seen in

Table 6-1 by the Clinical Events Committee.

Table 6-1. GUSTO Bleeding Criteria

GUSTO Bleeding Category	Definition
Severe or Life-Threatening	Intracerebral hemorrhage Substantial hemodynamic compromise requiring treatment
Moderate	Requiring blood transfusion but not resulting in hemodynamic compromise
Mild	Bleeding that does not meet the above criteria

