3.1 Data Analyses

The following data will be analyzed in this study:

- Antiplatelet therapy regimen
- Adverse events related to antiplatelet therapy
- Platelet reactivity testing results
- Moderate and Severe bleeding events utilizing GUSTO criteria
- All intracranial hemorrhages and delayed intracranial hemorrhages (>30 days post-procedure)

- Index procedure time
- Number of Pipeline™ Flex Embolization Device with Shield Technology™ utilized
- Device deployment success rate at target site
- Aneurysm occlusion at 6 months, 1 year and at last follow-up
- Recurrence and retreatment rates at 1 year post-procedure and at last follow-up
- The composite percentage of patients with modified Rankin Scale of 0-2 or no change from baseline at 1 year and at last follow-up.
- Occurrence of major stroke in the territory supplied by the treated artery or neurological death. Stroke events will be further characterized based on whether:
 - Event was caused by thromboembolic events
 - Event was caused by side-branch occlusion due to the study device

For the purposes of this study protocol, stroke is defined as a focal neurological deficit of presumed vascular origin persisting more than 24 hours from symptom onset and a neuro-imaging study or other quantitative study that does not indicate a different etiology. The 24-hour criterion is excluded if the subject undergoes cerebrovascular surgery or dies during the first 24 hours of symptom onset.

The definition includes:

- Subjects presenting with clinical signs and symptoms suggestive of subarachnoid hemorrhage, intracerebral hemorrhage, or cerebral infarction.
- Sudden loss or worsening of visual acuity due to retinal artery occlusion or retinal emboli.

The definition excludes:

- Slowly progressive cranial nerve palsies or progressive visual field deficits due to continued aneurysm growth.
- Stroke events in cases of blood disorders such as leukemia or external events such as trauma.

Stroke severity will be graded by the investigator as major or minor:

- Major Stroke: A stroke, which is present after seven days and increases the NIH Stroke Scale of the subject by ≥ 4 .
- Minor Stroke: A stroke, which resolves completely within seven days OR increases the NIH Stroke Scale of the subject by ≤ 3 .

Neurological death is any subject death due to an underlying neurologic cause.

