5.5 Data Collection

Eligible subjects will be treated with the Pipeline™ Flex Embolization Device with Shield Technology™.

Subjects will undergo standard of care follow-up visits. Data generated per standard of care will be collected for 1 year (± 8 weeks) beyond the index procedure. All follow-up visits and telephone calls during this time period will be recorded. A summary of the data to be collected is listed in **Table 5-1**.

In order to track compliance with antiplatelet therapy, subjects will be contacted at a minimum of approximately (± 14 days), 3 (± 30 days), 6 (± 6 weeks), and 12 (± 8 weeks) months post-index procedure and asked to confirm their current antiplatelet regimen and that all relevant adverse events (**Section 6**) have been reported.

A survey will be administered to all centers to collect their standard antiplatelet therapy regimen at the start of the study and annually.

Table 5-1. Data Collection

Time Period	Data to be Collected
Baseline	
• Relevant medical history and demographics• Aneurysm characteristics, symptoms and status (ruptured or unruptured)• Hunt & Hess Grade and WFNS (if ruptured)• Antiplatelet medication use within past 30 days• Other relevant concomitant medications• Platelet reactivity testing• NIH Stroke Scale (NIHSS)• Modified Rankin Scale (mRS)
Procedure	
• Relevant medications including antiplatelet regimen• Adverse events• Platelet reactivity testing• Procedure and fluoroscopy times• Study device information including side branches covered• Concomitant treatments• Deployment success at target IA• Imaging to be sent to the Core Lab*• Aneurysm occlusion• NIHSS• mRS
Post-Implant Follow-up	
• Relevant medications including antiplatelet regimen• Adverse events• Platelet reactivity testing• Imaging to be sent to the Core Lab*• Aneurysm occlusion• Retreatment• NIHSS• mRS

*All imaging taken (e.g., angiograms, CT, MR, rotational angiography with 3D reconstruction, cone-beam CT, etc.) should be provided to the Core Lab.

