An *Unanticipated Serious Adverse Device Effect (USADE)* is defined as a serious adverse device effect which by its nature, incidence, severity or outcome has not been identified in the current version of the risk analysis report. (ISO 14155:2011 3.42)

Note: Anticipated serious adverse device effect (ASADE) is an effect which by its nature, incidence, severity or outcome has been identified in the risk analysis report.

Severity:

- Mild: No limitation of usual activities, no therapy or only symptomatic therapy required to treat the injury or illness.
- Moderate: Some limitation of usual activities or specific therapy is required.
- Severe: Inability to carry out usual activities, hospitalization, emergency treatment, life threatening events, or death.

Causality Assessment:

The relationship between the use of the:

- Medical device (Medical device investigated in the Investigation) and
- The medical -surgical procedure (Procedure related events refers to the procedure related to the initial application of the investigational medical device only and therefore not to any other procedures or treatments applied later throughout the clinical investigation, for instance to treat (serious) adverse events.)

The occurrence of each adverse event shall be assessed and categorized according to five different levels of causality for which the following definitions shall be used to assess the relationship of the adverse event to the investigational medical device or procedure:

1. Not Related:

Relationship to the device or procedures can be excluded when:

- the event is not a known side effect of the product category the device belongs to or of similar devices and procedures;
- the event has no temporal relationship with the use of the investigational device or the procedures;
- the serious event does not follow a known response pattern to the medical device (if the response pattern is previously known) and is biologically implausible;
- the discontinuation of medical device application or the reduction of the level of activation/exposure - when clinically feasible – and reintroduction of its use (or increase of the level of activation/exposure), do not impact on the serious event;
- the event involves a body-site or an organ not expected to be affected by the device or procedure;

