7.10 Safety Evaluation

All summaries of Adverse Events will be primarily reported, but not limited to, for the ITT population.

The Clinical Events Committee (CEC) will be responsible for the review and adjudication of all adverse events per the definitions established in the CEC Charter/Manual of Operations.

Site Reported and CEC adjudicated events shall be summarized in incidence and frequency tables coded by System Organ Class (SOC) and MeDRA preferred term (PT).

A table reporting CEC adjudication disposition will be presented (Site Reported, CEC adjudicated).

CEC adjudicated Adverse Events will be mapped to preferred terms and body systems using the Medical Dictionary for Regulatory Activities (MedDRA) coding dictionary. The number and percentage of subjects experiencing Adverse Events will be summarized by system organ class and preferred term for all Adverse Events.

CEC adjudicated Adverse Events will be presented by system organ class and preferred term.

Summaries of CEC adjudicated AEs by the maximal severity (Mild, Moderate and Severe), relatedness (e.g., to the study device, procedure, anti-platelet therapy.), seriousness (serious, non-serious) and timing (Peri-procedural- Day 0, Acute- day 1-30 and Delayed, Day 31-Study Exit) shall be presented.

Causality Assessment (Relatedness)

CEC adjudicated relationship of each adverse event will be presented as follows:

- Device: Medical device: (Medical device investigated in the Investigation)
- Procedure: The medical -surgical procedure on day 0
- Anti-platelet therapy: Related to the anti-platelet agent therapy, that is required per standard of care for treatment.

Missing and Partial Adverse Event Dates

The recorded dates for adverse events are important for an accurate tabulation of both events and patients, and required for the following:

1. Defining the start of the event
2. Designation of unique adverse event occurrences recorded intra-patient.

Completely missing or partially missing adverse event dates will be imputed as follows:

- If the adverse event start date is completely missing the adverse event will be counted to the date of the study procedure.
- If the adverse event start date is partially missing and the partial date is not sufficient to determine if the event occurred after the start of the study procedure, then the adverse event will be counted with a start date of the procedure date.

Summaries of Adverse Events

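### Antiplatelet-related adverse events are a reported outcome, but the protocol's collection list has no category for them, so their rate can be undercounted

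*Protocol*

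**What the plan says.** **The outcome.** Protocol 3.1 lists "Adverse events related to antiplatelet therapy" among the data to be analysed, and 9.4 repeats it. In both lists it is an item of its own, apart from GUSTO bleeding and from intracranial haemorrhage. SAP 4 plans adverse events by seriousness, with non-serious events named, and by relatedness to procedure, device or antiplatelet therapy. SAP 7.10 defines the third relatedness class: "Anti-platelet therapy: Related to the anti-platelet agent therapy, that is required per standard of care for treatment".

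**Collection.** Protocol 6 begins "The following Adverse events will be collected during the course of the study on the eCRFs" and gives five categories. Two of them are broad: "All Adverse Events (AE) with an underlying neurological cause (Neurological Adverse Events") and "All Bleeding Events". The others are device-related, procedure-related and serious events. Later the same section states that "All study AEs, as well as the treatment and follow-up required, should be documented" in the medical record and the eCRF.

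**Follow-up contacts.** Under Protocol 5.5, subjects contacted at about 1, 3, 6 and 12 months are "asked to confirm their current antiplatelet regimen and that all relevant adverse events" have been reported, with a pointer back to Section 6.

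**Causality.** Protocol 6.1 gives a five-level scale to "assess the relationship of the adverse event to the investigational medical device or procedure". It has no antiplatelet relationship.

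**Adjudication.** Protocol 8.1 has the CEC review the adverse events reported in the study, including their relatedness.

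**The concern.** The analysis plan promises a category of event that the collection rule does not require sites to enter. Because the outcome is listed separately from bleeding, and because the SAP tables include non-serious events, a reader of the report will take the antiplatelet-related rate as covering everything attributed to those drugs. As written, it covers only those antiplatelet-related events that also fall into one of five other categories. SAP 3 says the results may support a US indication evaluation, so the tables should not appear more complete than the collection behind them.

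**Working it through.** The documents give no expected rate of antiplatelet-related events, so there is no planned figure to reproduce. The check is to follow one event through the rules.

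**Step 1: test event.** A non-serious rash, attributed to an antiplatelet drug, two months after the procedure. It is an adverse event under the broad definition in Protocol 6.1.

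**Step 2: does any Section 6 category require it?**

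| Category | Required? | Reason |
|---|---|---|
| Neurological | No | The cause is not neurological |
| Device-related | No | Protocol 21 wants a strong temporal link to the device and a less likely alternative cause; here the drug is the cause, and 6.1 grades an event reasonably explained by another cause as unlikely |
| Procedure-related | No | Protocol 21 ties it to Day 0, and 6.1 excludes treatments applied later |
| Bleeding | No | There is no bleeding |
| Serious | No | Non-serious by construction |

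Gastrointestinal intolerance without bleeding gives the same result. The uncaptured set is therefore non-serious, non-bleeding, non-neurological, and neither device- nor procedure-related.

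**Step 3: is there another route in?** The scheduled contacts refer to the Section 6 list, so they do not widen it. The CEC sees only reported events, so its antiplatelet attribution under SAP 7.10 cannot reach one that was never entered.

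**Step 4: direction.** Protocol 9.1 and SAP 7.2 define the rate as x/N, with x the subjects with an event and N the analysis population. An unentered event can remove a subject from x but not from N. This mechanism can therefore only lower the rate or leave it unchanged.

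**Step 5: size, as illustration only.** Let p be the true share of subjects with an antiplatelet-related event, and u the share of those subjects whose only such events lie outside the five categories. Both are assumptions. Then

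expected observed rate = p × (1 − u).

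With N = 200 (the maximum enrolment), x = 200 × p × (1 − u), rounded to whole subjects, and exact Clopper-Pearson 95% intervals:

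| p | u | x | Observed rate | 95% CI |
|---|---|---|---|---|
| 5% | 0 | 10 | 5.0% | 2.4% to 9.0% |
| 5% | 10% | 9 | 4.5% | 2.1% to 8.4% |
| 5% | 25% | 8 (7.5 rounded) | 4.0% | 1.7% to 7.7% |
| 5% | 50% | 5 | 2.5% | 0.8% to 5.7% |
| 10% | 0 | 20 | 10.0% | 6.2% to 15.0% |
| 10% | 10% | 18 | 9.0% | 5.4% to 13.9% |
| 10% | 25% | 15 | 7.5% | 4.3% to 12.1% |
| 10% | 50% | 10 | 5.0% | 2.4% to 9.0% |
| 20% | 0 | 40 | 20.0% | 14.7% to 26.2% |
| 20% | 10% | 36 | 18.0% | 12.9% to 24.0% |
| 20% | 25% | 30 | 15.0% | 10.4% to 20.7% |
| 20% | 50% | 20 | 10.0% | 6.2% to 15.0% |

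At u = 0 there is no bias. The interval misses the assumed truth in two rows: p = 10% and p = 20%, both with u = 50%.

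**Step 6: causality targets.** Protocol 6.1 has the investigator judge device and procedure. SAP 7.10 tabulates CEC-adjudicated device, procedure and antiplatelet therapy. The third target is in the SAP only.

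**The case against.** The strongest reply is that little of interest is lost. Protocol 1.3 frames the antiplatelet question around thrombotic and haemorrhagic events, and the bleeding, neurological and serious categories capture most of those. A reader might infer that drug tolerability was a stated aim; the rationale does not say so. This part of the reply stands and limits the importance of the gap. It does not remove the mismatch, because 3.1 and 9.4 list the outcome without restricting it to those events.

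A second reply is that attribution is already provided. That is right: SAP 7.10 supplies it through the CEC. A reader might infer from 6.1 that nobody attributes events to antiplatelet therapy, or that the causality form leaves it out. The first is wrong, and the second cannot be checked because no such form is in the documents. What remains is that investigators are not asked for a judgement on which the CEC will rule.

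A third reply is that sites may enter these events anyway. Protocol 10.2 lists allergic reaction to medications or dye among the placement risks, so a reaction close to Day 0 could well be reported as device- or procedure-related, and 6.1 grades relatedness that cannot be assessed as possible. This stands for early events. It does not cover a late one clearly due to the drug. The sentence "All study AEs, as well as the treatment and follow-up required, should be documented" could also be read as covering every adverse event, but after an explicit list it more naturally means the listed ones. If sites read it differently, capture would vary by site.

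Finally, the outcome is neither primary nor secondary in the SAP, and Protocol 9.2 sets no success criterion. Limiting adverse event collection in a post-market observational study is a legitimate choice. That argues for a small correction rather than against one.

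**Conclusion.** The point holds as a minor inconsistency between what is collected and what is reported. Under the plan as written, an antiplatelet-related event outside all five Section 6 categories need not be recorded, and no later step recovers it, so the reported rate can be too low. The size is unknown: the table above rests on assumed p and u and shows only how the shortfall would scale.

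A reader might go further and conclude that all non-serious, non-bleeding antiplatelet events are lost. The documents do not support that, since such events are still required if they are neurological, device-related or procedure-related. Nor do they support stating as fact that the rate is too low, since it is unaffected if no subject has only uncollected events.

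The conclusion assumes that sites follow the Section 6 list literally and that entered events are attributed correctly. No primary or secondary endpoint is affected.

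**What to change.** Add all adverse events related to antiplatelet therapy as a sixth item in the Protocol 6 list, and add antiplatelet therapy as a third relationship in Protocol 6.1, so that the protocol matches SAP 4 and 7.10. The cost is two short protocol changes and slightly more adverse event entry at sites.

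SAP 5 and 7.7 describe some data collection in the past tense, so this may no longer be possible. In that case, label the outcome and its tables as antiplatelet-related events among the collected adverse event categories, and name the five categories in a footnote. That costs nothing in data collection and makes the reported rate match what was collected.
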